6.2.2. Total Number of Flares

The second key secondary endpoint is the number of flares during the 52-week DB period.

- Estimand strategy: Hypothetical ([Section 2.1.2.2](#)).
- Analysis Population: Evaluable-DB.
- Analysis method: Wilcoxon rank sum test stratified by age group, duration of the BID treatment in OL period, and ISGA score at randomization.
- Intercurrent events: intercurrent events include discontinuation of treatment.
- Reporting results: Median for each treatment group and median difference estimated by the Hodges–Lehmann method² along with the 95% CI, p-value from Wilcoxon rank sum test will be reported.

Participants will be ranked in descending order according to the number of flares adjusted for length of time in the DB period, and length of time in flare-free period, ie if participants have same number of observed flares, below conditions will be used as tie-breaker in sequence:

- Participants who prematurely discontinue the study for efficacy reasons (ie, discontinue due to lack of efficacy or AD worsening of AE for treated lesions) will be ranked below others;
- The participant with longer time in the double-blind maintenance period will receive a higher rank;
- The participant with longer time in flare-free period will receive a higher rank.

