9.2. Sample Size Determination

A total of 162 events will provide approximately 96% power to detect a 1.8 ratio of median time of being flare-free (hazard ratio of 0.556) in the first QD period between crisaborole and vehicle at a significance level of 0.05 (2-sided, log-rank test). To get 162 events (first flare), approximately 250 participants who are eligible responders will be randomized (ratio=1:1) into the double-blind maintenance period of the study. When 162 events are observed, the randomization will be stopped even if less than 250 participants are randomized. On the other hand, if 250 participants are randomized, but 162 events cannot be reached, more participants will be randomized.

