2.1.2. Estimands for Secondary Endpoints

2.1.2.1. Estimand 2

Estimand 2: The second estimand of the study for the secondary endpoint of number of flare-free days during the DB period is a hypothetical estimand. It includes the following 4 attributes:

- Population: Patients who are treated with crisaborole 2% BID up to 8 weeks and achieve response defined by the criteria in the protocol.
- Variable: Flare-free days during the DB period. It is the total days that the participant has no flare during the DB period for each participant.
- Intercurrent events: intercurrent events include discontinuation of treatment. Addressing intercurrent events for the duration of flare-free maintenance at each flare-free period is the same as that for the primary endpoint during the first flare-free period.
- Population-level summary: Difference in least-square means between crisaborole ointment, 2%, QD and vehicle QD for flare-free days over 52 weeks.

2.1.2.2. Estimand 3

Estimand 3: The third estimand of the study for the secondary endpoint of number of flares during the DB period is a hypothetical estimand. It includes the following 4 attributes:

- Population: Patients who are treated with crisaborole 2% BID up to 8 weeks and achieve response defined by the criteria in the protocol.
- Variable: number of flares during the DB period.
- Intercurrent events: intercurrent events include discontinuation of treatment.
- Population-level summary: Median difference between crisaborole ointment, 2%, QD and vehicle QD for number of flares over 52 weeks.

2.1.2.3. Estimand 4

Estimand 4: The fourth estimand of the study for the secondary endpoint of maintenance of pruritus response up until the onset of the first flare (ISGA ≥ 2) is a hypothetical estimand. It includes the following 4 attributes:

- Population: Patients who are treated with crisaborole 2% BID up to 8 weeks and achieved pruritus response defined as ≥ 2 , 3, or 4 points of improvement from OL baseline in respective pruritus scales (See Section 3.2.1).
- Variable: Duration of maintenance of pruritus response up until the onset of the first flare (ISGA ≥ 2).

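### Number of flares: the Hodges-Lehmann difference does not match the ranked test, and its 95% CI would usually include 0 even when that test is significant

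*SAP*

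**What the plan says.** **Test.** SAP 6.2.2 specifies a "Wilcoxon rank sum test stratified by age group, duration of the BID treatment in OL period, and ISGA score at randomization". What is ranked is a composite: "Participants will be ranked in descending order according to the number of flares adjusted for length of time in the DB period" and flare-free time. Where counts are equal, "below conditions will be used as tie-breaker in sequence": withdrawal for efficacy reasons, then time in the double-blind (DB) period, then flare-free time. Protocol 9.4.1.2 lists the same elements in another order, with the two time criteria first and efficacy withdrawal last.

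**Effect measure.** The same SAP section reports "Median for each treatment group and median difference estimated by the Hodges–Lehmann method" with a 95% CI, beside the Wilcoxon p-value. It does not say which values enter the Hodges-Lehmann calculation. Estimand 3 (SAP 2.1.2.2) gives "Variable: number of flares during the DB period" and, as the summary, "Median difference between crisaborole ointment, 2%, QD and vehicle QD for number of flares over 52 weeks". Protocol 9.1.1 uses the same summary.

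**Place in the plan.** SAP 5.1.1 tests this endpoint third, at 0.05, ahead of the pruritus subgroups. SAP 6.2.2 plans no mean count, flare rate or rate ratio. SAP Table 1 records that the annualized analysis was removed in version 4 in favour of observed data.

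**The concern.** The p-value and the interval printed beside it describe different things. The test uses flare count, the tie-breakers and the strata. The Hodges-Lehmann estimate, on its natural reading, is the median of all vehicle-minus-crisaborole differences in flare count. It uses neither tie-breakers nor strata, and makes no allowance for time observed.

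Flare counts are small integers, so this median can hardly move. It is 0 unless at least half of all vehicle-crisaborole pairs have strictly more flares on vehicle. A true reduction of about half a flare per participant has no value on that scale. The clinical study report could therefore show a significant result for number of flares next to an interval that includes no difference, and a reader could not recover how large the reduction was or how precisely it was estimated.

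**Working it through.** **1. Inputs from the documents.** Protocol 9.2: "A total of 162 events will provide approximately 96% power to detect a 1.8 ratio of median time of being flare-free"; hazard ratio 0.556; two-sided 0.05; about 250 randomized 1:1. Protocol 4.1: flare treatment in 4-week courses up to 12 weeks, with withdrawal if unresolved. DB period of 52 weeks. No flare rate, mean count or power is given for the number of flares.

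**2. The plan's own figure.** Schoenfeld power = Φ(√(162/4) × |ln 0.556| − 1.96) = Φ(6.364 × 0.587 − 1.96) = Φ(1.776) = 96.2%. The stated 96% is reproduced.

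**3. Implied flare-free proportions.** 162/250 = 64.8% with a first flare, so S_v + S_c = 2 × 0.352 = 0.704. With proportional hazards S_c = S_v^0.556, giving S_v = 0.246 (vehicle) and S_c = 0.458 (crisaborole) with no dropout. With exponential times the hazards are 1.40 and 0.78 per year.

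**4. Why the estimate sits between 0 and 1.** Pairs with a flare on vehicle and none on crisaborole: 0.754 × 0.458 = 0.346. To reach one half, a further 0.154 must come from pairs whose crisaborole participant flared (0.542 of pairs). So vehicle must have strictly more flares in 0.154/0.542 = 28% of those. That depends on repeat flares, and hence on how fast flares resolve, which the documents do not state for this trial.

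**5. Simulation.** Recurrent flares over 52 weeks, 125 per arm, hazard calibrated to 64.8% first flares unless stated; stratified Wilcoxon test on the SAP 6.2.2 ranking; Hodges-Lehmann estimate on counts with its order-statistic CI. Dropout (0-30%), gamma frailty variance (0-1), flare resolution and eight random strata are assumptions.

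| Scenario | Estimate = 0 | CI includes 0 |
|---|---|---|
| Base 1: 60/20/10% resolve at 4/8/12 weeks, no dropout or frailty | 67.5% | 99.1% |
| Base 2: same resolution, 20% dropout, frailty 0.5 | 72% | 99% |
| All flares resolve at 4 weeks | 44-60% | 94-99% |
| All resolve at 12 weeks | 74-78% | 99% |
| 40/20/20% resolve, 20% withdrawn | 81-91% | 99-100% |
| 84-day median (figure from the earlier long-term study, Protocol 4.2) | 96-100% | 100% |
| 275 randomized, 162 events | 83-88% | 99-100% |
| First-flare share 75% | 43% | 96-97% |
| First-flare share 80% | 28% | 91-93% |
| Hazard ratio 0.70 | 98% | 100% |

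In Base 1 mean flares were 1.16 (vehicle) and 0.70 (crisaborole), a difference of 0.46, and the test was significant in 98% of trials. In Base 2 the means were 1.40 and 0.90, and 93.5% were significant. Among significant trials alone the estimate was 0 in 67% and 70%, and the CI included 0 in 99% of both. When the estimate was not 0 it was exactly 1.

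**6. Other assumptions.** Separate simulations with an unstratified test agree on the interval at the planning rates (96-100% in one set). With an 80% first-flare share they put the CI including 0 at 80% and 95%, and in one the estimate was 0 in only 16%.

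**7. A count-scale alternative.** With a true ratio of 0.556 in every QD period, a rate-ratio model averaged 0.60 with log DB time as offset and 0.56 with flare-free QD time. DB time includes flare-treatment time, when no new flare can start.

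**The case against.** Several objections carry weight.

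- **A reader might infer that the estimate will almost always be 0.** The documents do not support that. They give no repeat-flare or resolution rates. Under central assumptions the estimate is one flare in a substantial minority of trials, and it is near-certain to be 0 only with slow resolution and many withdrawals, a lower first-flare share or a weaker effect.
- **The flare rate is inferred.** Protocol 9.2 uses 162 events to stop randomization, not follow-up, so the final first-flare share could exceed 162/250. The problem then weakens; at a 90% share one simulation had the CI including 0 in 61% of significant trials. The background figure of about 8 flares a year in moderate disease (Protocol 2.2) cannot serve as the trial rate, because it does not fit 162 first flares in 250 participants.
- **A reader might infer damage to the testing sequence, or to the effect the trial is sized for.** Neither follows. SAP 5.1.1 gates on p-values only, and the trial is sized on time to first flare.
- **Flare benefit is shown elsewhere.** Flare-free days have an LS mean difference with CI (SAP 6.2.1), and time to first flare has Kaplan-Meier proportions and medians (SAP 6.1.1). These stand, but neither measures the number of flares.
- **Use of raw counts is not written in SAP 6.2.2.** True, but Estimand 3 points to counts, and a composite rank has no flare scale on which to take a difference. An interval from 0 to 1 also still excludes more flares on crisaborole.

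**Conclusion.** The point stands as a should-fix reporting weakness in one key secondary endpoint. The firm part is the mismatch: the CI does not invert the test, and at the planning figures it includes 0 in about 94-100% of trials, even when the test is significant. The point estimate is less certain: 0 or one flare, and 0 in about 60-85% of trials under central assumptions (about 20-100% across all those tried). With an 80% first-flare share the CI includes 0 in about 80-95%. These figures rest on exponential or gamma-frailty recurrent flares, the design hazard ratio in every QD period, and assumed dropout and resolution. Type I error and the route to the pruritus tests are sound. The loss is confined to reading the size and precision of the reduction in number of flares.

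**What to change.** Keep the test and the testing sequence. In SAP 6.2.2, SAP Estimand 3 and Protocol Estimand 3, make the effect measures:

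1. The stratified Mann-Whitney (win) probability with 95% CI on the ranking that is tested, after reconciling the tie-breaker order between Protocol 9.4.1.2 and SAP 6.2.2.
2. Mean flares per arm and a flare rate ratio with 95% CI, from a negative binomial or robust Poisson model with the same three factors. Use log flare-free QD time as the offset if the target is the flare hazard on QD treatment. Otherwise use log DB time, and state that it includes flare-treatment time and attenuates the ratio.

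The Hodges-Lehmann difference may stay as a descriptive figure, with a statement that it is computed on counts.

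The cost is one extra model and wording in three places, with no new data. It brings back a time-adjusted measure beside the observed-count analysis preferred in SAP version 4, so the SAP should say why both are shown. Protocol 9.4 requires an amendment for major changes to key secondary analyses, so one may be needed. The change should be made before unblinding; a new summary chosen after seeing an interval that includes 0 would look post hoc.

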6.2.3. Maintenance of Pruritus Response until Onset of First Flare (ISGA ≥ 2)

The third key secondary endpoint is duration of maintenance of pruritus response. It is the time from randomization to the loss of pruritus response or first flare onset (ISGA ≥ 2) during the 52-week DB period for participants who are pruritus responders at randomization. Pruritus response is maintained if $\geq 50\%$ of pruritus reduction from OL baseline to randomization is not lost.

- Estimand strategy: Hypothetical ([Section 2.1.2.3](#)).
- Analysis Population: Evaluable-DB.
- Analysis method: Time-to-event analysis, Kaplan-Meier (product limit) method and log-rank test ([Section 5.2.4](#)).
- Intercurrent events: intercurrent events include discontinuation of treatment, first flare [ISGA ≥ 2]. If an event (eg, death, first flare [ISGA ≥ 2], lost to follow up, or end of study) occurs before loss of pruritus response for the first flare-free period, the duration of maintenance of pruritus response is the time from randomization to the first intercurrent event and is censored. When loss of pruritus response occurs first, the duration of maintenance of pruritus response is not censored.

- Reporting results: At each month, the proportion of participants who maintained pruritus response in the first flare-free period, time-to-event curve, median (95% CI) time of maintaining pruritus response, and number (%) of censored participants for each treatment group, and p-value from log-rank test will be presented.

The analysis will be performed separately for each age and pruritus response subgroups:

- ≥ 12 years of age with OL baseline Peak Pruritus NRS ≥ 3 and ≥ 3 points reduction from OL baseline to randomization in Peak Pruritus NRS.
- ≥ 12 years of age with OL baseline Peak Pruritus NRS ≥ 4 and ≥ 4 points reduction from OL baseline to randomization in Peak Pruritus NRS.
- 6- <12 years of age with OL baseline PRIS Scale ≥ 2 and ≥ 2 points reduction from OL baseline to randomization in PRIS Scale.
- 3 months- <6 years of age with OL baseline ORIS Scale ≥ 3 and ≥ 3 points reduction from OL baseline to randomization in ORIS Scale.
- 3 months- <6 years of age with OL baseline ORIS Scale ≥ 4 and ≥ 4 points reduction from OL baseline to randomization in ORIS Scale.

6.3. Other Secondary Endpoints

6.3.1. Maintenance of EASI Response

This endpoint is defined as $\geq 50\%$ of EASI total score reduction from OL baseline to randomization is maintained. Only data up to the first flare onset (ISGA ≥ 2) during the maintenance period will be used for analysis.

- Estimand strategy: Hypothetical ([Section 2.1.1](#)).
- Analysis Population: Evaluable-DB.
- Analysis method: Time-to-event analysis, Kaplan-Meier (product limit) method and log-rank test ([Section 5.2.4](#)).
- Intercurrent events: intercurrent events include discontinuation of treatment, first flare. If an intercurrent event (eg, death, dropout, loss to follow up, first flare, or end of study) occurs before loss of EASI response, the duration of maintenance of EASI reduction is the time from randomization to the first intercurrent event and is right censored.
- Reporting results: At each month, the proportion of participants maintaining $\geq 50\%$ EASI reduction before the first flare, time-to-event curve, median (95% CI) time of maintaining $\geq 50\%$ EASI reduction, and number (%) of censored participants for each treatment group, and p-value from log-rank test will be presented.

6.3.2. Maintenance of Dermatology Quality of Life Assessments

Maintenance of dermatology quality of life assessments is defined as the response achieved does not lose more than MCID. Only data up to the first flare onset during the DB period will be used for analysis.

- Estimand strategy: Hypothetical ([Section 2.1.1](#)).
- Analysis Population: Evaluable-DB.
- Analysis method: Time-to-event analysis, Kaplan-Meier (product limit) method and log-rank test ([Section 5.2.4](#)).
- Intercurrent events: intercurrent events include discontinuation of treatment, first flare. If an intercurrent event (eg, death, dropout, loss to follow up, first flare, or end of study) occurs before loss of dermatology quality of life response, the duration of maintenance of dermatology quality of life assessments is the time from randomization to the first intercurrent event and is right censored.
- Reporting results: At each month, the proportion of participants who maintained dermatology quality of life assessments before the first flare, time-to-event curve, median (95% CI) time of maintaining dermatology quality of life assessments, and number (%) of censored participants for each treatment group, and p-value from log-rank test will be presented.

The analysis will be performed separately for two age groups:

- Participants ≥ 16 years of age, Dermatology Life Quality Index (DLQI).
- Participants 4- <16 years of age, Children's Dermatology Life Quality Index (CDLQI).

MCID is not available for Infant's Dermatitis Quality of Life Index (IDQoL) for participants 3 months - <4 years of age. Maintenance of dermatology quality of life assessments will not be performed for that age group.

6.3.3. Maintenance of Patient Oriented Eczema Measure (POEM)

This endpoint is defined as the response achieved does not lose more than MCID. Only data up to the first flare onset during the DB period will be used for analysis.

- Estimand strategy: Hypothetical ([Section 2.1.1](#)).
- Analysis Population: Evaluable-DB.
- Analysis method: Time-to-event analysis, Kaplan-Meier (product limit) method and log-rank test ([Section 5.2.4](#)).

- Intercurrent events: intercurrent events include discontinuation of treatment, first flare. If an intercurrent event (eg, death, dropout, loss to follow up, first flare, or end of study) occurs before loss of POEM response, the duration of maintenance of POEM is the time from randomization to the first intercurrent event and is right censored.
- Reporting results: At each month, the proportion of participants who maintained POEM response before the first flare, time-to-event curve, median (95% CI) time of maintaining POEM response, and number (%) of censored participants for each treatment group, and p-value from log-rank test will be presented.

The analysis will be performed separately for two age groups:

- ≥ 12 years of age (participant reported POEM).
- 3 months- <12 years of age (proxy POEM).

6.3.4. Endpoints during Flare Treatment Period

6.3.4.1. Severity of Flare on Investigator's Static Global Assessment Score

- Analysis Population: Evaluable-DB.
- Method: Descriptive summary for categorical endpoint; Descriptive summary for continuous endpoint.
- Reporting results:
 - ISGA as a categorical endpoint: the number and percent of participants for the first flare period and each time point by ISGA categories and DB treatment assignment group and overall group;
 - ISGA as a continuous endpoint: the number of participants, mean, standard deviation, median, minimum, maximum for the first flare period and each time point by DB treatment assignment group and overall group for observed and change from initiated of the first flare period. The summary is performed by the time point relative to the start of first flare period (ie, Weeks 0, 4, 8, 12 in the first flare period).

6.3.4.2. Severity of Flare on Eczema Area and Severity Index Score

- Analysis Population: Evaluable-DB.
- Method: Descriptive summary for continuous endpoint.
- Reporting results: The number of participants, mean, standard deviation, median, minimum, maximum for the first flare period and each time point by DB treatment assignment group and overall group for observed and change from initiated of the

first flare period. The summary is performed by the time point relative to the start of first flare period (ie, Weeks 0, 4, 8, 12 in the first flare period).

6.3.4.3. Duration of Flare Periods

- Analysis Population: Evaluable-DB.
- Method: Descriptive summary for continuous endpoint. The average duration of flare periods (sum of durations/number of flares) will be calculated for each participant, then summarize the average duration.
- Reporting results: The number of participants, mean, standard deviation, median, minimum, maximum by DB treatment assignment and overall.

